## **Exclusion criteria:**

- Contraindication to treatment with anti-CD20 antibodies, including being seropositive for HBsAg or HIV antibody or T-spot (or Quantiferon-Gold) positive
- Ever received B-cell depleting antibodies (rituximab, ocrelizumab, ofatumumab), alemtuzumab, daclizumab, mitoxantrone or hematopoietic stem-cell transplant
- Female who are pregnant, nursing or unwilling to use contraception up to six months after the second course of the infusion (or 12 months after the first infusion)
- Treatment with steroids in the past 30 days
- Clinically unstable medical or psychiatric disorders at the time of screening that require acute treatment as determined by the PI

**Study duration:** 2.5 years after the last dose of B-cell depleting antibody, ocrelizumab.

**Description of study intervention:** Participants will receive two courses of treatment with ocrelizumab, an FDA-approved medication for treatment of relapsing MS. The ocrelizumab infusions will not be

Version: 2.0

Date: 3/8/2019

repeated after these two courses. Patient will be monitored for the return of clinical or MRI disease activity for at least 2.5 years after the last dose ocrelizumab. Immune cell phenotype and B-cell tolerance characteristics will be assessed before start of the treatment with ocrelizumab and 12-18 months after the second course of ocrelizumab infusion.

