## Investigational plan

### Study design

This is an open label, single-arm study of anti-CD20 antibody, ocrelizumab in people with relapsing MS. Patients who fulfill the eligibility criteria will undergo blood draw for collection of peripheral blood mononuclear cells (PBMC). Participants will receive two infusions of ocrelizumab (300 mg) two weeks apart and then six months later (one infusion of 600 mg of ocrelizumab), according to the medication label and the standard of care. Baseline brain, cervical and thoracic MRI will be obtained about 12 weeks after the first course of treatment. Participants will be followed with clinical visits at least twice a year (or more frequently, if needed) and brain MRI (every six months) and cervical and thoracic spine MRI, at least annually, up to two and a half years after the baseline MRI.

The trial design is depicted in the following diagram:

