**Screening visit:** PI or designee will explain the study consent to study participants, and the study visit assessments will occur after the study participants sign the consent form. Screening visit procedures include review of eligibility criteria, physical exam, neurological examination, collecting vitals, blood work for assessing eligibility (liver function tests, complete blood count, Hepatitis- B surface antigen, Hepatitis- B core antibody, HIV antibody, lymphocyte subset including CD19+ B-cells, total IgG and IgM and urine pregnancy test) and blood draw (for collecting PBMCs), and completion of Neuro-QoL adult item banks. Study participants will be enrolled into the study after the study physician confirms participants' eligibility to move forward with the study.

Obtaining the B-cell depleting antibody (ocrelizumab) and all the subsequent study visits and MRIs are part of routine and standard clinical care. If the B-cell depleting medication is not approved by the participants' insurance policy, the patient will be excluded from the study.

**MRI procedures:** MRI scans will be performed at one of the Hopkins Radiology facilities at 3T. Conventional T2/FLAIR/T1-weighted images as well as post-contrast T1-weighted images of the brain will be obtained at months 3 (baseline), 12, 18, 24 and 30. Conventional T2/STIR/T1-weighted images as well as post-contrast T1-weighted images of the cervical and thoracic spinal cord will be obtained at months 3 (baseline), 12 and 24. Similar to the standard of care, brain, cervical or thoracic spine MRIs may be done as needed if the patient develop symptoms that could be suggestive for an MS relapse (based on the evaluation by a study neurologist). The MRI scans will be read by an attending radiologist at Johns Hopkins University, and these readings will be used for making decisions regarding the presence of new T2 or Gd-enhancing lesions suggestive for re-emergence of the radiological disease activity.

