## Outcomes:

**Primary outcome:** The primary endpoint (the failure event) of this study is the time to return of disease activity after the third month post-first-infusion, objectively demonstrated by development of new T2 hyperintense lesions or Gd-enhancing lesions on the MRI or a clinical relapse. A relapse is defined as new or worsening neurologic symptom(s) with an objective change on the EDSS of at least 1.5 points for participants with baseline EDSS scores of 0 or 0.5 and at least 1-point change for participants with EDSS of 1 or more, as determined by the *examining neurologist*. Symptoms must have been attributable to MS, last  $\geq 48$  hours, been present at normal body temperature, and preceded by at least 30 days of clinical stability. If a new or worsening neurological symptom did not fulfil the above-mentioned criteria, but was associated with a corresponding new or enhancing lesion on the MRI that is done in 30 days after the start of that symptom, it is still considered a clinical relapse.

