**Assessment of T and B-cell phenotypes and function at baseline and 18-24 months post-B-cell depletion**

The assessment T and B-cell phenotypes and function and analysis of the central and peripheral B-cell tolerance checkpoints, as well as measurement of cytokines will be done at Yale University. 30 milliliters of blood will be drawn from the participants before start of the treatment with ocrelizumab (at the screening visit) and 12 or 18 months after the second course of ocrelizumab infusion (month 18 or 24 of the study) and will be sent to Yale University for the analyses explained below.

We will investigate the T and B-cell phenotypes in the blood samples from the participants in the study, pre-treatment and after they repopulate their peripheral B-cells likely at either 18- or 24-months time points. We will follow the frequencies of  $CD3^+CD4^+CD25^{hi}CD127^{lo}FOXP3^+$  Tregs, circulating  $CD3^+CD4^+CXCR5^+PD-1^+$  Tfh cells increased in several autoimmune diseases, and other CD4+ and CD8+ naïve and memory T cell subpopulations. We will also assess the production of several cytokines including IL-2, IL-4, IL-6, IL\_10, IL-17, IL-21, IFN-gamma and TNF-alpha by Tregs and other T cell subsets after activating PBMCs with phorbol-12-myristate-13-acetate (PMA) and ionomycin for 4 hours in the presence of GolgiStop (BD Biosciences) and intracellular staining with specific monoclonal anti-cytokine antibodies as previously reported by our laboratory. Hence, we will determine if the abnormal production of IL-17 and IFN-gamma previously identified in Tregs from people with MS or their elevated Tfh frequencies are corrected after two courses of anti-B-cell deletion. In addition, we will assess *in vitro* the suppressive function of Tregs from people with MS before and after B-cell deletion. Indeed, Tregs from people with MS have been reported to display decreased suppressive function and we will therefore be able to determine if ocrelizumab can normalize Treg function and if this feature is associated with long-term disease suppression.

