## Statistical analysis

We will describe the demographic, clinical characteristics and MRI data of all participants before treatment with the B-cell depleting agent. We will report the proportion of participants who experience the primary endpoint of the study (return of the disease activity) and the time to failure event, using a Kaplan-Meyer curve. Proportion of patients with clinical relapse, new MRI activity or disability progression will separately be reported. Quality of life data will be analyzed using linear mixed effect models.

To look at the association between long-term response to B-cell depletion therapy and autoreactivity of B-cells at different stages of development, we will use logistic regression and Cox proportional hazards models with failure or time-to-failure event as the outcome variable and the above-mentioned proportion of auto-reactive B-cells at different stages of development and the change in proportions before and after treatment as the predictor variables. Failure event as defined in the Aim 1 is the return of disease activity after the third month post-first-infusion, objectively demonstrated by development of new T2 hyperintense lesions or Gd-enhancing lesions on the MRI or a clinical relapse that is confirmed with an objective change in the neurological examination or a corresponding new or enhancing lesion on the MRI that is obtained after the onset of symptoms.

Version: 2.0

Date: 3/8/2019

Using paired t-test, we will compare the frequency of autoreactive mature naïve B-cells, Treg and Tfh cells and cytokine production before treatment with ocrelizumab and after the B-cell repopulation.

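### The change in autoreactive B-cells is known only at month 18 or 24 but is used to predict failure counted from month 3, so early failures precede their own predictor

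*Combined protocol and SAP*

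**What the plan says.** The Statistical analysis section plans logistic regression and Cox models with failure, or time to failure, as the outcome. The predictors are the proportion of autoreactive B-cells at different developmental stages and "the change in proportions before and after treatment as the predictor variables". It does not say whether the proportion entered on its own is the pre- or the post-treatment value.

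The same section starts the clock early: "Failure event as defined in the Aim 1 is the return of disease activity after the third month post-first-infusion". Under Primary outcome, failure is "objectively demonstrated by development of new T2 hyperintense lesions or Gd-enhancing lesions on the MRI or a clinical relapse", with no minimum lesion count.

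The section on T and B-cell phenotypes puts the post-treatment draw at "12 or 18 months after the second course of ocrelizumab infusion (month 18 or 24 of the study"), and the Schedule of events agrees. The sample is meant to be taken "after they repopulate their peripheral B-cells likely at either 18- or 24-months time points". Under MRI procedures, "images of the brain will be obtained at months 3 (baseline), 12, 18, 24 and 30", with extra scans if symptoms suggest a relapse.

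On what follows a failure, the documents differ:

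- Known Potential Risks says ocrelizumab is restarted in patients whose disease activity returns.
- Treatment stop rules requires two new T2 lesions, two enhancing lesions or specified kinds of relapse, and equates restart with stopping the study.
- Discontinuation of study intervention says everyone who started treatment is followed.

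No section gives a landmark, a time-dependent covariate, delayed entry, or a rule for samples taken after failure or restart.

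**The concern.** A Cox or logistic model with a fixed covariate treats that covariate as known when the clock starts. Here it becomes known 15 or 21 months later. For a participant who fails at the month-12 scan, the model reads a month-18 or month-24 measurement as a predictor of something that has already happened.

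This is more than untidy order, because the outcome can act on the predictor. The marker is measured on B-cells and the restarted drug depletes B-cells. A failure can therefore change the later sample, or remove it if B-cells have not repopulated or if restart ends participation. An association could then appear because failure or retreatment altered the marker, not because corrected tolerance preceded disease control.

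These models are the plan's only stated method for linking tolerance correction to clinical response. The introduction names biomarkers of long-term suppression as the next step, and the Sample size section looks ahead to a larger study. A misread association could be carried forward as a candidate biomarker.

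**Working it through.** **The plan's own figure.** The only power statement (more than 90%, Sample size section) concerns the pre/post t-test. It reproduces: about 100% if the ± values are SDs, and at least 99.6% if they are standard errors from an assumed 5–30 source subjects. It does not cover the regression models, for which the plan gives no figure.

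**1. Share of the at-risk window before the draw.** The clock starts at month 3. The end of follow-up can be read three ways: month 30 (Schedule of events); month 33, from "up to two and a half years after the baseline MRI" (3 + 30); or month 36, from "for at least 2.5 years after the last dose ocrelizumab" (6 + 30). Share = (draw − 3)/(end − 3).

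| End of follow-up | Draw at month 18 | Draw at month 24 |
|---|---|---|
| 30 | 15/27 = 56% | 21/27 = 78% |
| 33 | 15/30 = 50% | 21/30 = 70% |
| 36 | 15/33 = 45% | 21/33 = 64% |

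Of the four scheduled post-baseline brain scans (12, 18, 24, 30), one strictly precedes a month-18 draw and two precede a month-24 draw.

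**2. Expected failures before the draw.** Assumptions, not in the documents: 40% of 10 participants fail by month 30, with constant hazard −ln(0.6)/(30 − s) from s = 3, 6 or 12. For s = 3 the hazard is 0.5108/27 = 0.01892 per month, so before month 18 the count is 10 × (1 − exp(−0.01892 × 15)) = 2.47.

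| Of 4 expected failures (s = 3 / 6 / 12) | Month 18 | Month 24 |
|---|---|---|
| Onset before the draw | 2.47 / 2.25 / 1.57 | 3.28 / 3.18 / 2.89 |
| Known from an earlier scheduled scan | 1.57 / 1.20 / 0.00 | 2.47 / 2.25 / 1.57 |
| Onset after the draw | 1.53 / 1.75 / 2.43 | 0.72 / 0.82 / 1.11 |

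**3. Effect on error.** Null simulation, 4,000 trials per setting, n = 10. The marker is unrelated to failure, and an assumed shift is added only to failures known before the draw who restart. Permutation tests were applied to the Cox score and to the failure versus non-failure contrast. Ranges span both tests, s = 3, 6 and 12, and both draw times. Rejection at a nominal 5%, with 40% failure:

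| | Scheduled-scan detection | Detection at onset |
|---|---|---|
| No shift | 4–5% | 4–5% |
| 1 SD, all restart | 5–15% | 7–20% |
| 2 SD, all restart | 5–36% | 12–53% |
| 1 SD, half restart | 4–8% | 5–9% |
| 2 SD, half restart | 5–14% | 6–18% |

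With 20% failure and all restarting, the ranges are 3–7% (1 SD) and 3–19% (2 SD) for scheduled-scan detection, and 4–10.5% and 8–29% for detection at onset.

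A separate simulation used the large-sample Cox score test, hazard from month 3, 40–60% failure, and a shift in every pre-draw failure. It gave 5–6% with no shift, 18–22% at 1 SD and 45–58% at 2 SD. With n = 100 the 1 SD figure rose to 90–99%, while a landmark analysis from the draw stayed near 5%. A larger study therefore makes the problem worse.

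**4. If restarted participants give no post sample.** Error is not inflated, but events are lost. With scheduled-scan detection, modelled failures fall from 4 to 4 − 1.57 = 2.4 up to 4.0 (month 18), or 4 − 2.47 = 1.5 up to 2.4 (month 24).

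**The case against.** The strongest reply is that the reversed order does no harm by itself: with no shift, rejection stays at 4–5%. All inflation comes from an assumed shift of unknown size. The assay also needs repopulated B-cells, so a participant restarted on ocrelizumab may more often give no usable sample than a shifted one, and missing samples do not inflate error. The 40% failure rate has no source. The introduction cites one patient among more than 180 with enhancing lesions 18 months after the last infusion. The plan names no test or significance level for these models, speaks only of association, and calls itself a pilot. Finally, excluding every pre-draw failure also drops those never retreated.

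Much of this stands. It limits the size of the problem and keeps it below a major finding. The cited figure counts enhancing lesions at one time point, so it is not a cumulative rate of the composite failure used here, but it does not support 40% either. If hazard begins only at month 12, no scheduled-scan failure precedes a month-18 draw.

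It does not remove the defect. Whether restarted participants yield shifted samples, missing samples or neither is exactly what the plan leaves open. Calling the result an association does not say in which direction it runs. A failure that was not retreated is still earlier than its own predictor; such participants belong in a descriptive listing, where their values remain visible.

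**Conclusion.** The concern holds and should be fixed. As written, the plan relates failures to a marker measured after some of them occurred, and possibly after retreatment. That follows directly from the documents' dates and needs no assumption beyond reading the silence on timing as it stands.

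Confidence in the size of the bias is low. Under the illustrative 40% failure rate, error ranges from nominal (no shift, or missing samples) to 53% (2 SD shift, all failures detected at onset and all restarting). How many failures restart cannot be settled from the documents, because the failure definition and the restart statements do not match.

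The defect touches the post-treatment level and the change, in both the logistic and the Cox models. Post-restart samples can also enter the paired t-test.

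**What to change.** Reword the Statistical analysis section:

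1. Models with the clock from month 3 use only the pre-treatment proportion.
2. The post-treatment level or change is related to failure only from each participant's draw date, among those failure-free (counting the scan due at that visit) and not retreated by then, and is labelled exploratory. Where too few failures follow the draw, list post values descriptively by prior failure and restart status.
3. Each post sample carries a restart flag. Report the paired t-test with the numbers of missing and post-restart samples, and add a sensitivity analysis without the post-restart samples.

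Separately, Known Potential Risks, Discontinuation of study intervention, Primary outcome and Treatment stop rules must be reconciled on who restarts, and on whether those participants stay in follow-up and give the post sample.

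The cost is wording and one flag per sample, with no extra visits or blood. The downside is sparsity: early failures leave the modelled comparison and appear only in the listing. At 40% failure by month 30, the expected events after the draw are 1.5–2.4 (month 18) or 0.7–1.1 (month 24). The binomial chance of 0 or 1 event is 26–53% or 69–84%. With 40% failing by month 33 or 36 instead, it is 18–46% or 46–74%. In this pilot the descriptive listing will often be the realistic result.

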## **Objectives**

- To determine whether two courses of treatment with ocrelizumab is associated with long-term suppression of disease activity in people with highly active relapsing MS.
- To test if two courses of treatment with ocrelizumab corrects the B-cell tolerance defects in patients with relapsing MS.

**Study design:** Open-label intervention.

**Number of patients:** 10

**Target population:** Adult patients with relapsing MS

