## Specific aims and study overview

**Aim1: To determine whether two courses of treatment with ocrelizumab is associated with long-term suppression of disease activity in people with highly active early relapsing MS.**

We hypothesize that only two courses of treatment with ocrelizumab in subjects with early relapsing MS will stop the disease activity, as measured by new T2 or Gd-enhancing lesions on brain and spinal cord MRI, even long after B-cell repopulation in the blood. In an open label unblinded trial, we will enroll 10 patients with relapsing MS and with at least two Gd-enhancing lesions on the brain and spinal cord MRI and treat them with two courses of ocrelizumab and follow them clinically and radiologically for at least two and a half years.

**Aim 2: To test if two courses of treatment with ocrelizumab corrects the B-cell tolerance defects in patients with relapsing MS.** We hypothesize that B-cells repopulating after a two course-treatment with ocrelizumab will NOT contain an elevated proportion of autoreactive clones observed pre-treatment. In the patients recruited in aim 1, we will harvest pre-treatment and post-repopulation peripheral B-cells and assess early B-cell tolerance checkpoints by testing the reactivity of recombinant antibodies cloned from single B-cells.

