### Secondary objective

[figure not shown]
To determine whether these two courses of treatment with ocrelizumab correct the B-cell tolerance defects in patients with relapsing MS.

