#### [Analysis of the central and peripheral B-cell tolerance checkpoints](#)

Single CD19+CD10hiCD21-/loIgMhiCD27 new emigrant/transitional and CD19+CD10+CD21+IgM+CD27 mature naïve B-cells will be isolated from the blood of these patients before and after treatment and frequencies of polyreactive, HEp-2 reactive and anti-nuclear clones will be determined as previously described. In brief, Ig heavy and light chain genes will be amplified by RT-PCR and 20-30 immunoglobulin genes from single new emigrant/transitional and mature naïve B-cells will be cloned and expressed in vitro. Recombinant antibodies will be tested for HEp-2 reactivity and polyreactivity by ELISAs and anti-nuclear reactivity using indirect fluorescence assay on HEp-2 slides as previously described. Recombinant antibodies will be considered polyreactive when they recognized all three antigens tested individually (dsDNA, insulin, and LPS) using supernatants tested at 1 $\mu$ g/ml antibody concentrations and three 1:4 dilutions in PBS as reported. In HEp-2 and polyreactivity ELISAs, ED38 recombinant antibody will be used as positive control. Hence, we will determine if B-cell depletion can correct the impaired removal of developing autoreactive B-cells in the periphery of people with MS and is associated with disease suppression.

**Safety and adverse effect monitoring:** Potential participants will have lab work done (liver function tests, complete blood count, Hepatitis- B surface antigen, Hepatitis-B core antibody, HIV antibody, lymphocyte subset including CD19+ B-cells, total IgG and IgM and urine pregnancy test) as part of routine clinical care to assess for study eligibility and as the baseline for future comparison. Patients who are positive for Hepatitis-B surface antigen (HBsAg) or Hepatitis-B core antibody (HBcAb) will be excluded from participation.

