## Sample size

We selected to recruit 10 participants in this open-label, non-controlled study. We limited the number of participants for two reasons: The pre- and post-infusion analysis of B-cell tolerance is expensive and time-consuming, and we could accommodate the analysis of only 20 samples (10 pre and 10 post-infusions samples) during the proposed time of the study. We also wanted to make sure that we would observe a prolonged drug-free absence of disease activity in a subset of participants, before recruiting a larger group of patients for a potential larger study.

The sample size is supported by our previous studies of central and peripheral B-cell checkpoints in patients with autoimmune diseases and healthy control subjects in which we had found that the frequency of autoreactive mature naïve B-cells was  $48.9 \pm 3.06\%$  in patients and  $20.1 \pm 0.9\%$  in healthy donors. Assuming that the frequency of autoreactive cells among post-treatment repopulated B-cells will be similar to normal controls, our proposed sample size of 10 subjects per group before and after treatment would give us more than 90% power to detect a significant difference with an  $\alpha$  of 0.05 with a 2-sided Student's t-test. The analysis of each individual is very labor intensive and costly but fortunately, significant findings on the establishment of B-cell tolerance can be obtained with a relatively small number of subjects.

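### Aim 2 asks whether treatment corrects the B-cell tolerance defect, but the only pre/post analysis tests for any change, and nothing compares post-treatment values with normal

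*Combined protocol and SAP*

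**What the plan says.** Three places state the objective as correction. The Synopsis (Objectives) has "To test if two courses of treatment with ocrelizumab corrects the B-cell tolerance defects in patients with relapsing MS". The Secondary objective is to determine whether treatment will "correct the B-cell tolerance defects in patients with relapsing MS". The section on the central and peripheral tolerance checkpoints promises: "we will determine if B-cell depletion can correct the impaired removal of developing autoreactive B-cells in the periphery of people with MS". Aim 2 (Specific aims and study overview) turns this into the hypothesis that repopulating B-cells "will NOT contain an elevated proportion of autoreactive clones observed pre-treatment".

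The Statistical analysis section has one pre/post comparison: "Using paired t-test, we will compare the frequency of autoreactive mature" naïve B-cells, together with Treg, Tfh and cytokine measures. Its logistic and Cox models relate autoreactivity to return of disease activity. They do not address normalisation.

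A normal value does appear, under Sample size: 20.1 ± 0.9% in healthy donors against 48.9 ± 3.06% in patients, from earlier work on "checkpoints in patients with autoimmune diseases and healthy control subjects in which we had found" those frequencies. It is used only for the power statement: "Assuming that the frequency of autoreactive cells among post-treatment repopulated B-cells will be similar to normal controls". Healthy controls are otherwise named among the planned measurements only for the Ki67/KREC work on proliferation history, with no analysis stated.

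**The concern.** The null hypothesis of a paired t-test is zero mean change. A partial fall and a full return to normal both contradict it, so a significant result does not tell them apart. The question matters because the background section offers normalisation of the peripheral checkpoint as the possible reason for long-term suppression of disease. No text says that p<0.05 will be read as correction. The difficulty is that the plan contains no analysis that could support that word, so the reference value and its interpretation would be chosen after the results are known.

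**Working it through.** **The plan's own figure.** Sample size claims more than 90% power for 10 before and 10 after, two-sided α = 0.05. The assumed difference is 48.9 − 20.1 = 28.8 points. The ± values are not labelled SD or standard error.
- Read as SDs: pooled SD = √((3.06² + 0.9²)/2) = 2.26, and two-sample t power exceeds 99.9%.
- Read as standard errors from 10 or 20 reference subjects (assumed numbers): power again exceeds 99.9%. It falls below 90% only for much larger reference groups (97% at 50 subjects, 77% at 100).

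So the claim reproduces under most readings, but it is power against zero change when normalisation is assumed to be complete.

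**How far short of normal can a significant result be?** The checkpoint section plans "20-30 immunoglobulin genes from single new emigrant/transitional and mature" naïve B-cells. It is unclear whether 20–30 applies to each subset or to both together, so I take m = 20–30 or 10–15 mature naïve clones per sample. Assumptions: the 48.9% applies to this MS cohort, and clone sampling is the only noise.

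- SD of one patient's frequency: 100·√(p(1−p)/m)
- Just-significant fall: 2.262·√(SDpre² + SDpost²)/√10, where t(0.975, 9) = 2.262 and SDpost is taken at the resulting mean
- Half-gap mean: (48.9 + 20.1)/2 = 34.5%, a fall of 14.4 points; power from the noncentral t

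Example, m = 20: SDpre = 11.18 and SDpost = 10.84, so the fall is 2.262 × 15.57/3.162 = 11.1 and the post-treatment mean is 37.8%.

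| Clones | Just-significant fall | Mean left | Multiple of 20.1% | Half-gap power |
|---|---|---|---|---|
| 10 | 15.5 | 33.4% | 1.66 | 46% |
| 15 | 12.8 | 36.1% | 1.80 | 63% |
| 20 | 11.1 | 37.8% | 1.88 | 75% |
| 30 | 9.1 | 39.8% | 1.98 | 89% |

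**Sensitivity.**
- More variation: at difference SDs of 20 and 25 points (assumed), half-gap power is 53% and 37%.
- Lower baseline: at 40% (assumed), the just-significant fall is 8.8 to 14.8 points, leaving 25.2% to 31.2% (1.25 to 1.55 times healthy). Half-gap power is 26% to 63%.
- ± read as SDs: 2.262·√(3.06² + 0.9²)/√10 = 2.3 points would be significant, or 3.1 points with 3.06 at both times.

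**Would an interval against 20.1% help?** Simulated 95% intervals for the post-treatment mean, n = 10, same noise assumption:

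| Clones | Wholly above 20.1%, true 34.5% | Includes 20.1%, true 27.3% (three-quarter closure) | Half-width, true 20.1% |
|---|---|---|---|
| 10 | 77% | 73% | 9.1 |
| 15 | 92% | 60% | 7.4 |
| 20 | 98% | 47% | 6.4 |
| 30 | 99.8% | 29% | 5.2 |

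When the true mean is 20.1%, the interval lies wholly above it in about 2% of trials.

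**The case against.** Aim 2 is the one place that turns correction into a hypothesis, and its wording can be read as a within-patient contrast, which the paired test does address. This is a 10-patient pilot, the objective is secondary, and the healthy value is already printed for readers to compare. The sizes above rest on assumptions, and half-gap power runs from 26% to 89%. That a significant fall need not be normalisation is a point of logic that needs none of them.

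Part of this stands. The paired test is not wrong, and no single magnitude is established. But the Synopsis, the Secondary objective and the checkpoint section ask about correction without the pre-treatment qualifier, and the power statement assumes values like those of normal controls. Because the plan claims power for this comparison, pilot status does not excuse leaving its interpretation open.

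A second objection concerns the remedy: an interval rule with no tolerance could label a trivial excess over 20.1% as failed correction. That needs post-treatment SDs of about 0.9 to 3.06. With 30 clones, sampling noise alone gives 100·√(0.201 × 0.799/30) = 7.3 points, and fewer clones give more, so intervals that tight are not expected.

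Two limits remain. The healthy value is historical, with no donor numbers or matching given. And the interval can rule correction out more readily than it can establish it.

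**Conclusion.** The concern holds. Followed exactly, the plan can show that autoreactive B-cells fell, but it has no analysis that separates a partial fall from correction. The gap itself is certain from the text. Its size is illustrative: with the 48.9% baseline and clone-sampling noise only, a significant result is compatible with a mean 1.7 to 2.0 times the healthy value, or 1.25 to 1.55 times from a 40% baseline. Between-patient variation would raise the fall needed for significance, lower half-gap power, and widen the proposed interval. The clinical primary endpoint is unaffected. This should be changed, since the second objective cannot be answered as planned.

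**What to change.** In Statistical analysis:

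- Keep the paired t-test, described as the test of reduction.
- Add the post-treatment mean frequency of autoreactive mature naïve B-cells with its 95% CI, and its difference from the laboratory's healthy-donor value. Carry that value's own uncertainty into the difference wherever the laboratory can supply it. If ±0.9 is a standard error, this widens the standard error of the difference by only about 2–7% (10 clones: √(4.01² + 0.9²) = 4.11; 30 clones: √(2.31² + 0.9²) = 2.48).
- State the reading in advance. A significant paired test supports a reduction. An interval wholly above the healthy value means not fully corrected. An interval that includes it means compatible with correction, quoted with the upper limit as the excess not ruled out.
- For Treg, Tfh and cytokines, report change only unless the laboratory supplies healthy values, because the documents give none.

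A formal verdict of correction is optional and not recommended as the default. It would need a bound set from healthy-donor data before the post-treatment assay results are seen. At assumed post-treatment SDs of 8 to 12 points, a 34.5% bound would pass three-quarter closure in 40% to 72% of trials, and a 25% bound would fail 59% to 79% of fully normalised trials.

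The cost is a few sentences, with no new samples, visits or assays. The price is that a partial fall can no longer be called correction, and that with 10 patients the question may stay open.
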